Our central hypothesis is that participation in a 6-week community-based program will significantly increase: (a) healthy dietary behavior patterns and basic knowledge of nutrition; (b) physical activity levels; and (c) the organization of collective/shared family mealtimes. Consequently, excessive weight gain or weight rate among participant children will be slower compared to non-participants. This project is based on the *Abriendo Caminos* pilot study that demonstrated an increase in healthy eating behaviors by building on elements of a traditional diet ([name], Wiley et al. 2013), and preliminary data (presented at conferences and under review) indicate improvements in family-meal quality and increased physical activity.

The *Abriendo Caminos* program was developed using best-practice principles for working with Hispanics, including: i) focus on the whole family at the site of intervention; ii) optimizing existing family strengths, building on everyday practices such as shared mealtimes, and iii) emphasis on low literacy, with accessible materials and focus on oral presentations and cultural relevance including emphasis on healthy traditional foods such as cactus (*nopales*), amaranth and legumes (beans). The **immediate beneficiaries** of our obesity prevention intervention will be children 6 to 18 year-old from Hispanic-heritage families.

This integrated project will address knowledge gaps about successful implementation of childhood obesity prevention programs in Hispanics, improve outreach to this population, and seek improvements in recruiting, educating, and retaining Hispanic students in higher education.

Our research, education and extension objectives are interdependent and mutually enriching.

Research objectives are to: 1) Identify prevailing factors influencing effective interventions on Hispanic children's unhealthy weight gain; 2) Adapt (culturally/regionally) and implement the proven *Abriendo Caminos* curricula to prevent childhood overweight/obesity (prevent excessive weight gain or weight rate); 3) Refine and expand our evidence-based nutrition curriculum (e.g. expanding focus on consumption of culturally relevant, affordable, and healthy foods such as legumes/dry beans).

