4	Salt and Sugars Objective: Develop a realistic understanding of the necessity of controlling salt and sugar intake and learn strategies for doing so	Reducing Sibling Conflict During Meals Objective: Learn that sib conflict is "normal;" learn strategies to reduce sib conflicts, increase positive affect and show genuine concern; scrapbook	Other forms of Cardiovascular Activity Objective: Experience other simple and fun types of CV activity such as Zumba or salsa dancing					
5	Fats and Protein Objective: Understand the value of lean protein and healthy fat and the necessity of monitoring fat intake	Emphasizing Family Traditions Objective: Understand that traditions in families of origin have meaning and value for today; scrapbook	Resistance Training Objective: Experience other simple methods of resistance training					
6	Wrap up, review and fiesta Objective: Share healthy recipes, food, and fellowship	Building New Family Traditions Objective: Work to create new traditions that have meaning and strengthen family; share scrapbooks	Combining Resistance and Cardiovascular Activity in an everyday workout Objective: Learn ways to optimize time and effort to get some resistance and cardio at home					

Experimental design

Our collaborator sites, plus Illinois, represent a variety of Hispanic cultures and communities across the country. The *Abriendo Caminos* curriculum will be implemented using a random control trial design. Materials and validated outcome measures will be adapted to meet the specific needs of each site. Adaptation of program will be based on assessment of needs in each participating region and results of focus groups conducted prior to implementation (Aim 1, measurable outcome). Implementation of intervention will be staggered, beginning in Illinois where we have developed the program and then in California where an original team member will lead the effort. Whole families will be recruited for participation, targeting those with one or more children in the age range of 6 to 18 year-olds and involving as many members as possible. Data to evaluate measurable outcomes will be collected at baseline (pre-intervention), after the 6-week education program (post-intervention) and 6 months after completion of the program (maintenance). Hispanic and bilingual Extension educators, local community agency staff, and trained college-students will act as facilitators to deliver the program.

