Measures: Basic nutrition knowledge for parents and children (i.e. portion sizes) and food consumption surveys (to evaluate weekly consumption of specific items), based on NCCOR adapted instruments will be used (McKinnon, Reedy et al. 2012). The Mealtime subscale of the Family Ritual Questionnaire (Fiese and Kline 1993) be used to assess mealtime organization. We will use the long-form of the International Physical Activity Questionnaire (IPAQ) to assess the parent and children's physical activity levels, as it has been shown that the short form (SF) is not useful in Latin-American populations (Hallal, Gomez et al. 2010). Other measures, and sources, are presented in **Table 5.**

Table 5 – Instruments to evaluate impact of intervention program (*=main outcomes)

Construct

Demographics and Socioeconomic Status

Socio-cultural factors (e.g.; Hispanic origin, immigration history, acculturation, acculturative stress)

Perceptions of Child Weight and Health

Intentions to Modify Health Environment

Family Health Behaviors and Access (includes food security and access to grocery stores)

Family Ritual Questionnaire

*Higher levels of family mealtime organization

Dietary Patterns for children and parents

*Increased consumption of fruits, vegetables and legumes

*Reduced consumption of sugar-sweetened beverages

Home Environment and Food Environment

Physical Activity (International Questionnaire, Long Form)

*Increased minutes of daily physical activity

*Prevent excessive weight gain or maintain healthy weight in Hispanic Children 6-18 yr-old for up to 6 months

Expected outcomes. We expect that participation in a 6-week community-based program will result in the following:

- ✓ Increased consumption of fruits, vegetables and legumes
- ✓ Reduced consumption of sugar-sweetened beverages
- ✓ Increased minutes of daily physical activity
- ✓ Higher levels of family mealtime organization
- ✓ Prevent excessive weight gain/maintain healthy weight in Hispanic children (6 to 18 yrs)

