Dissemination. This integrated project will result in an effective, low-cost obesity prevention intervention (available in Spanish and English) that can be disseminated by Extension professionals and community agency staff in other locations across the US, including external advisory board members' coalitions (i.e. LULAC, professional societies). Ultimately, widespread implementation of the *Abriendo Caminos* program will help improve health outcomes in difficult-to-engage stakeholders at elevated risk of poor health and will reduce the prevalence of childhood overweight and obesity in Hispanics. This sustainable multi-state intervention will also strengthen Extension and USDA connections with Hispanic population across the country.

Approach.

The Implementation and Evaluation phase will execute and test the effectiveness of a community workshop-based curriculum Abriendo Caminos to prevent childhood obesity and promote healthy nutrition and life-style behaviors among low income, low literacy Hispanic-heritage families across the country. We will recruit whole families (n=250) with one or more children in the target age range and involve as many members as possible.

Data will be collected at baseline (pre-intervention), after the 6-week education program (post-intervention) and 6 months after completion of the program (maintenance). Several mechanisms are in place to minimize attrition on the follow-up. Implementation will be staggered, as indicated before. Participating sites will conduct the program only after **Aim 1** is completed (Focus groups, survey) to tailor lessons before implementation of the **Abriendo Caminos** curriculum, as indicated in **Table 5**.

Table 5. Participants in intervention (control)*.								
Site	FY-2s	FY-2f	FY-3s	FY-3f	FY-4s	FY-4f	FY-5s	
IL	10(10)	20 (20)	20 (20)					50(50)
CA	10(10)	20 (20)	20 (20)					50(50)
IA				10(10)	20 (20)	20 (20)		50(50)
PR					10(10)	20 (20)	20 (20)	50(50)
TX					10(10)	20 (20)	20 (20)	50(50)
Total	20 (20)	40(40)	40(40)	10 (10)	40(40)	60(60)	40(40)	250(250)
*Note: The experimental unit is the family.								

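### Does the central hypothesis, worded as participants against non-participants, set aside the randomised comparison?

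*Protocol*

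**What the plan says.** The central hypothesis in the Project Narrative has two parts. The behavioural part reads "Our central hypothesis is that participation in a 6-week community-based program will significantly increase: (a) healthy dietary behavior patterns and basic knowledge of nutrition", followed by physical activity and shared mealtimes, and names no comparison group. The weight part does name one: "Consequently, excessive weight gain or weight rate among participant children will be slower compared to non-participants".

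Under Specific Aim 2, Experimental design, the protocol says that the "curriculum will be implemented using a random control trial design". Under Expected outcomes it returns to the language of participation, "We expect that participation in a 6-week community-based program will result in the following", and lists five directional results without a comparator.

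Under Approach, the table of planned numbers is headed "Table 5. Participants in intervention (control", with the control count in brackets after each intervention count. It shows 250 intervention and 250 control families, equal in every site and period, with the footnote "Note: The experimental unit is the family". The protocol defines neither participant nor non-participant.

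**The concern.** Read literally, a family that is randomised to the workshop and never comes is a non-participant. Grouping families that way would put no-shows with the controls and leave only attenders on the intervention side. Families who manage six 2-hour sessions probably differ from those who do not, so the comparison would no longer be protected by randomisation and would tend to favour the programme.

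The behavioural outcomes raise a second worry. Words such as increased, reduced and higher, with no comparator, could be satisfied by a before-after gain among attenders. Diet and activity are measured by questionnaire, so season, repeated testing and socially desirable answers could produce such a gain without any programme effect. Removing these influences is the purpose of the control arm.

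The table heading appears to add weight. If it calls families in both arms participants, then non-participants cannot be the protocol's name for its controls.

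**Working it through.** **What the wording refers to**

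1. *Object of participation.* In the central hypothesis and under Expected outcomes, participation is in the 6-week programme, not in the trial. Control families do not receive the programme, so in that sense they are non-participants.
2. *Available comparison group.* Experimental design declares a randomised controlled trial, and the table under Approach supplies the controls. No other untreated group appears anywhere in the protocol. A reading in which non-participants are controls plus intervention no-shows needs a rule that the protocol does not contain.
3. *Table heading.* "Participants in intervention (control" can be read as participants in the intervention, with control counts in brackets. That fits participant meaning intervention family. It can also be read as covering both arms. The heading is ambiguous and settles nothing.
4. *Behavioural outcomes.* The expected results are directional. They name no control group, but they also name neither a before-after test nor attenders. In the hypothesis, the weight effect is presented as following from the behavioural effects, and it is stated against a comparison group.
5. *Analysis rules.* The protocol contains no analysis by attendance, no before-after test and no rule for reassigning or dropping families who do not attend.

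**The protocol's own figure**

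Sites: 5 × 50 = 250. Periods: 20 + 40 + 40 + 10 + 40 + 60 + 40 = 250. The bracketed control counts are identical, so the table's 250 (250) is reproduced. The text under Approach says "We will recruit whole families (n=250) with one or more children in the target age range". This agrees with the table if it means the intervention arm, though the text does not say so. The calculations below take 250 per arm from the table.

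**What an attendance comparison would cost, if one were planned**

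From the protocol: 250 families per arm. Assumed, because the protocol gives no values: no true effect, SD 1, independent families, two-sided 5% test, a fraction f = 0.3 of intervention families not attending, and non-attenders d = 0.3 SD worse than attenders.

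- Attenders: 250 × 0.7 = 175 families, mean 0.
- Non-attenders: 250 × 0.3 = 75 families, mean −0.3.
- Controls: 250 families, mean −f × d = −0.3 × 0.3 = −0.09, because they contain the same mix of families.

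*As allocated:* intervention mean = 0.7 × 0 + 0.3 × (−0.3) = −0.09, the same as the controls. The difference is 0 and the error rate is 5%.

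*Attenders against controls plus non-attenders:* pooled mean = (250 × (−0.09) + 75 × (−0.3)) / 325 = −45 / 325 = −0.138, a spurious difference of 0.138 SD. SE = √(1/175 + 1/325) = 0.094. The false-positive rate is 0.315. Over 20–40% non-attendance and 0.2–0.5 SD it runs from 0.11 to 0.83.

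*Attenders against controls, non-attenders dropped:* difference 0.09, false-positive rate 0.150.

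*Before-after in 250 families with a background shift of 0.1 SD of the change score:* z = 0.1 × √250 = 1.58, false-positive rate 0.353.

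*Full attendance, with no control family attending:* the participation contrast and the randomised contrast are the same comparison, and the rate is 0.05.

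The arithmetic is sound, but apart from the as-allocated case and full attendance, each result describes an analysis that appears nowhere in the protocol.

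**The case for a change.** The strongest case for the concern is that this is the only statement labelled the central hypothesis, and that no passage restates any outcome as assigned intervention against assigned control. The one comparator named for any outcome is non-participants, and the behavioural outcomes have none. The protocol itself foresees difficulty: it lists factors that keep parents from attending meetings, and it expects some teenagers to be brought against their will. An analysis plan takes its hypothesis from the protocol, so vague wording could later let an attender or before-after analysis be presented as prespecified.

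Part of this stands. The wording is loose, the terms are undefined, and naming the randomised arms would be clearer. But wording that does not exclude a poor analysis is not wording that prescribes one. The hypothesis comes in a project narrative, ahead of the design section, and the design section says that the trial is randomised and controlled. Listing expected benefits without repeating the control group each time is ordinary style in such a trial.

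The details that would close the gap are analysis as allocated, adjustment for baseline, site and cycle, and a supportive role for attendance analyses. A protocol commonly leaves these to the statistical analysis plan. Their absence here is not an error in the protocol.

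**Conclusion.** The concern does not hold. The natural reading of the hypothesis is programme families against randomised control families, and nothing in the protocol contradicts that reading or directs a different analysis. The false-positive rates of 15%, 32%, 35% and up to 83% are correct for the analyses they describe, but they depend on assumed non-attendance, assumed differences between attenders and non-attenders, or an assumed background shift. None of them is an error rate of this plan.

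The conclusion rests on two premises: that participation refers to the programme, as the hypothesis itself says, and that no attendance-based or before-after analysis is prescribed elsewhere. The second is true of the protocol. It cannot be checked for a statistical analysis plan that is not available. What remains is imprecise narrative wording, with no stated rule that would give a wrong result.

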Extension objectives are to: 1) Refine and develop low-cost and readily implementable curriculum that will be made freely available across the country for use by Extension and community educators, 2) Train Extension professionals, lay community members, agency staff, and college-students as facilitators to deliver the curriculum and Extension staff to serve in a train-the-trainer capacity in the future (supporting sustainability); and 3) Test the implementation of alternative culturally-appropriate instructional methodologies with implications for other Extension programming.

CURRENT SITUATION/SIGNIFICANCE.

The high prevalence of early onset obesity is of great concern from a public health perspective (**Table 1**), in part because of the strong persistence of childhood obesity into adulthood and given relation of childhood obesity to adult metabolic complications and other clinical comorbidities.

Obesity has many health, social, psychological, and economic consequences including a shorter life expectancy than previous generations and increased healthcare costs accounting for 6.7 to 10.7% of total U.S. annual medical expenditures and up to \$147 billion dollars (Trogdon, Finkelstein et al. 2012). Because up to 70% of obese adolescents grow up to become obese adults (Whitaker, Wright et al. 1997, Freedman, Khan et al. 2001, Wang, Chyen et al. 2008), there are high costs to health and to the country. Still, recent data suggest that there is a window of opportunity to effectively impact the weight status of a child during childhood (Danielsson, Kowalski et al. 2012).

AGE group:	2-19 y (all)			6-11 y (target population)			12-19 y (target population)		
	ALL	NHW	Hispanic	ALL	NHW	Hispanic	ALL	NHW	Hispanic
Overweight or Obese (BMI for Age ≥85th Percentile of the CDC Growth Charts)									
All	31.8	28.5	38.9	34.2	29.4	46.2	34.5	31.2	38.1
Boys	32.0	27.8	40.7	33.2	26.5	48.7	35.1	31.5	39.6
Girls	31.6	29.2	37.0	35.2	32.7	43.6	33.8	31.0	36.5
Obese (BMI for Age ≥95th Percentile of the CDC Growth Charts)									
All	16.9	14.1	22.4	17.7	13.1	26.1	20.5	19.6	22.6
Boys	16.7	12.6	24.1	16.4	8.8	28.6	20.3	18.3	23.9
Girls	17.2	15.6	20.6	19.1	17.9	23.4	20.7	20.9	21.3

Table 1: Prevalence of High BMI (≥ 85th%'tile of the CDC growth charts) for Children, 2 to 19 years, by sex and age. Contrast of all race/Hispanic origin groups (ALL) with Non-Hispanic Whites (NHW) and Hispanic origin (Hispanic) groups, US (2011-2012). Modified from: (Ogden, Carroll et al. 2014).

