- a) Prevent development of overweight/obesity [success is defined as prevention of excessive weight gain / maintenance of healthy weight status] in 6 to 18 year-old children from Hispanic-heritage families for up to 6 months, and
- b) Evaluate the impact of our evidence-based nutrition and behavioral modification curriculum in weight maintenance and obesity prevention in Hispanic children and their families.

Introduction

In 2009, the Robert Wood Johnson Foundation's *Salud America* initiative called for the development of multifaceted, culturally relevant, and demonstrably effective interventions to impact childhood obesity in Hispanic families (http://www.rwjf.org). This was in response to the data demonstrating that Hispanics face a number of health disparities, such as heightened risk for type 2 diabetes, coronary heart disease, and obesity (National Hispanic Caucus of State Legislators). Many Hispanics live in neighborhoods with limited access to healthy foods (Larson, Story et al. 2009), and studies have consistently reported that Hispanic children's daily consumption of fruits and vegetables fall short of recommendations (Health and Human Services and USDA 2005;(Basch, Zybert et al. 1994, Cullen, Baranowski et al. 2000, Nicklas, Jahns et al. 2013).

Sugar-sweetened beverages (SSBs) are the largest contributor of added sugar and a considerable source of calories in the diets of children and adolescents in the United States (Reedy and Krebs-Smith 2010), and SSB intake has been associated with obesity and type 2 diabetes (Ebbeling, Feldman et al. 2006, Fiorito, Marini et al. 2009, Malik, Popkin et al. 2010, Ebbeling, Feldman et al. 2012, Ebbeling 2014). Consumption of SSBs may also serve to take the place of other healthier foods (Malik, Popkin et al. 2010). The consumption of sugar-sweetened beverages is disproportionately high among those with low-income (Han and Powell 2013). Hispanics may believe that culturally relevant drinks made with sugar, water and fruit (aguas frescas) have healthy homemade ingredients (Bogart, Cowgill et al. 2013).

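### The starred weight outcome joins two non-equivalent goals without saying how they combine, and on its likely readings it does not match the hypothesis of slower weight gain

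*Protocol*

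**What the plan says.** The weight outcome is worded in three places under Specific Aim 2 of the protocol:

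- Objective a): "Prevent development of overweight/obesity [success is defined as prevention of excessive weight gain / maintenance of healthy weight status". The two goals are separated by a slash.
- Table 5 (instruments), starred as a main outcome: "Prevent excessive weight gain or maintain healthy weight in Hispanic Children 6-18 yr-old for up to 6 months". Here the connective is *or*.
- Expected outcomes list: "Prevent excessive weight gain/maintain healthy weight in Hispanic children (6 to 18 yrs". The slash again.

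The central hypothesis in the Project Narrative is comparative: "excessive weight gain or weight rate among participant children will be slower compared to non-participants". The opening of Specific Aim 2 names both prevalence and excessive gain as things to reduce.

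Recruitment is by age, "targeting those with one or more children in the age range of 6 to 18 year-olds", and no baseline weight limit is stated. The last visit is "6 months after completion of the program (maintenance". The note to the participants table (also numbered 5) says "The experimental unit is the family".

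Table 1, row "Overweight or Obese (BMI for Age ≥85th Percentile of the CDC Growth Charts", gives 46.2% for Hispanic children aged 6-11 and 38.1% for those aged 12-19. The protocol does not say what counts as excessive gain.

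**The concern.** Avoiding excessive gain and keeping a healthy weight are different tests. The first looks at change, the second at which side of a cut-off the child ends on. A child can pass one and fail the other, so the outcome has no fixed meaning until the protocol says how they combine.

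On the one connective the protocol spells out, *or*, the gain test has no force for a child who starts at a healthy weight unless that child crosses the 85th percentile. Yet excessive gain is what the central hypothesis is about. Children who start at or above the cut-off face a stricter test. A real slowing of gain would then be partly invisible in the group that is probably the larger one, and the main weight result could not be read as a direct answer to the stated hypothesis.

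A cut-off for excessive gain set in a SAP would change the size of the problem but would not say how the two goals combine.

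**Working it through.** **1. What each reading implies.** 'Healthy' is taken here as below the 85th percentile, the Table 1 cut-off.

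| Reading | Starts healthy, gains excessively, stays below the 85th | Starts at or above the 85th |
|---|---|---|
| Either goal suffices (the *or* of the starred outcome) | Meets it | Must avoid excessive gain |
| One goal per baseline group | Meets it | Must avoid excessive gain |
| Both goals required | Fails | Must also reach a healthy weight |
| Two names for one thing | Not possible: the goals classify this child differently | – |

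Example: moving from the 50th to the 80th percentile is a rise of 0.842 - 0 = 0.84 z. It meets the first two readings however excessive gain is defined.

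**2. How many children.** Assume Table 1 applies to those enrolled, one child per family and 250 families per arm (the participants table totals 250 with 250 controls).

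- At or above the 85th: 0.462 × 250 = 115.5; 0.381 × 250 = 95.25, so about 95-116 per arm.
- Below it: 0.538 × 250 = 134.5; 0.619 × 250 = 154.75, so about 135-155. This is an upper bound for healthy weight, since it includes underweight.

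**3. Illustration of the loss.** The protocol has no power calculation to reproduce. Everything below except the Table 1 percentages and the 250 is assumed.

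*Baseline.* A normal z-score is fitted to the two Table 1 cut-offs (85th = 1.036 z, 95th = 1.645 z). This gives mean 0.93, SD 1.12 at 6-11 years and mean 0.63, SD 1.35 at 12-19 years. Without treatment there is no mean change. The baseline to follow-up correlation r is 0.90 or 0.95. Excessive gain is a rise above t = 0.2, 0.3 or 0.5 z. There are 200 or 250 children per arm, and clustering is ignored.

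*No treatment effect (simulated).* Either/or success is 81-95% overall, 88-97% in children starting below the 85th percentile and 71-94% in those at or above it. Of all children with excessive gain, 40-55% still meet the outcome.

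*Shift detectable with 80% power on baseline-adjusted z:* d = 2.80 × SD × √(1 - r²) × √(2/n). Across scenarios d is 0.09-0.17 z.

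*One scenario in full: 6-11 years, r = 0.90, t = 0.2, n = 250.*

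- d = 2.80 × 1.12 × 0.436 × 0.0894 = 0.122.
- Gain-only rule: the SD of change is 1.12 × √(2 × 0.10) = 0.501. Success is Φ(0.2/0.501) = 0.655 in controls and Φ(0.322/0.501) = 0.740 with the shift. SE = √[(0.655 × 0.345 + 0.740 × 0.260)/250] = 0.0409. Power = Φ(0.085/0.0409 - 1.96), about 0.54.
- Either/or rule (simulated): 0.807 to 0.862. SE = √[(0.807 × 0.193 + 0.862 × 0.138)/250] = 0.0331. Power = Φ(0.055/0.0331 - 1.96), about 0.38.

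Here dichotomising costs about 80 - 54 = 26 points, and *or* a further 54 - 38 = 16.

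*All 24 scenarios (two age groups, two r, three t, two n).*

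| Measure | Power for the same shift |
|---|---|
| Baseline-adjusted z-score | 80% (by construction) |
| Gain-only yes/no | 28-56% |
| Either/or yes/no | 19-38% |

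Within matching scenarios, *or* removes about 9-25 points of a total loss of 42-61. At least half of the loss is due to dichotomising in every scenario. With r down to 0.80, either/or power is 19-43%; with no regression to the mean it is 22-45%.

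**The case against.** The best defence is that no responder rule exists. Nowhere does the protocol score an individual child. The other starred items are directions of effect, and the stated unit is the family. The bracket in objective a) may be a loose gloss, and its slash may mean one goal for each baseline group. A child who goes from the 50th to the 80th percentile has not become overweight, which fits the opening words of that objective. Cut-offs can come in a SAP.

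Much of this stands. Only the starred outcome says *or*, and child-level scoring is an inference from the fact that weight status belongs to a child. But the defence does not settle how the goals combine, and assigning one goal per baseline group gives the same result for the healthy-weight child as *or* does. It also leaves the outcome out of line with a hypothesis about slower gain.

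Two stronger readings should be resisted. A reader might infer that little room is left to show benefit. The protocol gives no success rates to support that, and another set of assumed rates leaves 9-28 points of room under either/or against 20-50 under a gain-only rule. A reader might also blame *or* for the whole fall from 80% to 19-38%. The gain-only comparison shows that it explains the smaller part.

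**Conclusion.** The point holds as a defect of definition. The main weight outcome rests on two non-equivalent goals joined by a slash in one place and *or* in another, with no rule for combining them. On the two most natural readings, children who start at a healthy weight can gain excessively and still meet it, while the 38.1-46.2% at or above the 85th percentile (if enrolment resembles the national Table 1) face a different test. Neither reading matches the central hypothesis.

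The cost attributable to *or* is about 9-25 points of power in the illustration. That rests on assumed correlations, thresholds and a uniform shift, so it compares measures and is not a statement about this trial's power. The documents do not support a claim that the trial cannot show a weight benefit. The change is worth making because it is cheap and matches the hypothesis.

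**What to change.** In objective a) of Specific Aim 2 and in the starred line of the instruments table, make the main weight outcome the child's BMI-for-age z-score (CDC charts, as in Table 1) at the existing visit 6 months after programme completion. Compare it between the randomised arms in all enrolled children aged 6-18, adjusting for baseline z-score and allowing for siblings, since the family is the experimental unit.

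Keep incident overweight/obesity, in children below the 85th percentile at baseline, as a secondary outcome. Align the expected outcomes list, the central hypothesis in the Project Narrative, goal a) of Aim 2 in the list of specific aims, and the opening of Specific Aim 2. The other starred outcomes need no change on this account.

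The cost is protocol wording. The measure needs only the height, weight, age and sex that any BMI-for-age classification needs, at a visit already planned. The downside is that a mean z-score difference is less intuitive than a success rate; the secondary outcome partly offsets this. If the sponsor prefers a yes/no outcome, the minimum is to state which goal applies to which baseline group. That would remove the ambiguity but not the loss from dichotomising or the mismatch with the hypothesis.

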We will *implement and evaluate* the *Abriendo Caminos* community workshop-based curriculum in five different locations (California, Illinois, Iowa, Puerto Rico, and Texas). Materials for program implementation and validated outcome measures will be regionally adapted (**Table 4**). The nutrition curriculum will be also refined and expanded to promote consumption of inexpensive and culturally-familiar foods such as dry beans (legumes) and other regional or cultural foods (cactus-*nopales*). The physical activity curriculum will promote fun activities that the entire family can enjoy including walking and folk dancing (or Zumba) and adapted to participating location. Our management plan and regular meetings with Advisory Board will contribute to minimize difficulties and challenges to achieve this aim.

This proposal implements a community-based participatory program (CBPP) approach, and integrates socio-cultural and socio-ecological theories with elements of the health belief model to focus on behavior change through multiple levels of influence: individual, interpersonal, and at community level.

POTENTIAL IMPACT OF THE OVERALL PROJECT AND EXPECTED OUTCOMES.

The proposed multi-function integrated Research, Education, and/or Extension project will result in an effective, low-cost **childhood obesity prevention intervention** (available in Spanish and English) to be disseminated by Extension professionals and community agency staff in other locations across the US. Many Extension services across the country have been under increasing pressure to reduce staff and engage in a train-the-trainer model of program delivery. We will strengthen relationships with relevant community partners as well as grow the Extension "brand" as a provider of research-based, effective, affordable, and culturally relevant materials. The proposed project aims also to train staff in the 5 participating states in effective methods for achieving these goals and provide a model that is applicable more broadly.

Ultimately, implementation of the *Abriendo Caminos* program will **Clear the Path to Hispanic Children's Health** and improve outcomes in difficult-to-engage stakeholders at elevated risk. It will reduce the prevalence of childhood overweight and obesity and contribute to their well-being.

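### Does the protocol contradict itself by recruiting 250 families in the text and 250 plus 250 in the participant table?

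*Protocol*

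**What the plan says.** The prose of Specific Aim 2 gives the number of families once, under Approach: "We will recruit whole families (n=250) with one or more children in the target age range". It does not say whether this covers one arm or both.

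The participant table in the same section is headed "Participants in intervention (control", so the first number in each cell is the intervention arm and the number in brackets is the control arm. It lists five sites across seven enrolment periods. Every site ends at 50 intervention and 50 control, and the grand total is 250 and 250. Its footnote fixes the unit: "The experimental unit is the family".

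Two other places bear on the reading. Under Experimental design for Aim 2, the protocol says that the "curriculum will be implemented using a random control trial design". The central hypothesis in the project narrative expects that "weight rate among participant children will be slower compared to non-participants".

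**The concern.** In a randomised trial the control families are recruited too. A bare recruitment figure would therefore ordinarily be taken as the whole trial. Read that way, the sentence gives 250 families where the table gives 500, a difference of a factor of two in the same section. The footnote rules out the easy explanation that one place counts families and the other counts individuals.

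The number of randomised units is a basic figure of any trial. If sentence and table really disagreed about it, a reader could not tell whether the study was planned with 125 or 250 families per arm. Anyone taking the size from the prose alone would report half of what the table plans.

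**Working it through.** **Inputs.** All come from the protocol, Specific Aim 2, Approach: the figure of 250 in the sentence and the cells of the participant table. The control entry equals the intervention entry in every cell, so one set of sums serves for both arms.

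**Sum by site, per arm.** Each site enrols in three periods:

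10 + 20 + 20 = 50 families

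Five sites: 5 × 50 = 250 families per arm.

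**Sum by enrolment period, per arm.**

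| Period | Contributing sites | Families per arm |
|---|---|---|
| FY-2s | IL 10, CA 10 | 20 |
| FY-2f | IL 20, CA 20 | 40 |
| FY-3s | IL 20, CA 20 | 40 |
| FY-3f | IA 10 | 10 |
| FY-4s | IA 20, PR 10, TX 10 | 40 |
| FY-4f | IA 20, PR 20, TX 20 | 60 |
| FY-5s | PR 20, TX 20 | 40 |
| Total | | 250 |

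20 + 40 + 40 + 10 + 40 + 60 + 40 = 250. The table's own totals are reproduced in both directions.

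**Both arms.** 250 + 250 = 500 families, and 500 / 5 = 100 per site.

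**Comparison with the sentence.**

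- Read as one arm: 250 against 250, exact agreement.
- Read as both arms together: 250 / 500 = 0.50, half the table's plan. That would be 250 / 5 = 50 families per site across both arms, or 250 / 2 = 125 per arm. The row and column sums exclude this, because all the entries would have to be wrong together.

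**Which reading fits the text.** The sentence contains no word such as total or overall, so the conflict arises only if the reader supplies one. The central hypothesis contrasts participating children with non-participants, so there participation means attending the programme. Experimental design describes recruiting whole families for participation, and the Approach sentence goes on in the same vein about involving as many family members as possible. That suits families who come to a whole-family workshop. On this usage 250 is the first number of the table's grand total.

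**Does anything depend on the figure?** The protocol states no significance level, power, effect size, standard deviation or dropout rate, so no sample-size result is derived from 250 or from 500. The enrolment schedule is set cell by cell in the table, for both arms.

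**The case for a change.** The strongest case for a correction is that the wording does not settle the matter. Recruiting normally includes controls. The preceding sentence is about testing effectiveness, which needs a control group, and the schedule of data collection that follows is not limited to one arm. The table heading applies the word participants to both groups, which weakens the argument from the hypothesis. Nowhere does the protocol say that 250 is a per-arm figure, so the reader has to infer it.

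All of that stands as a comment on drafting. It shows that the sentence is unlabelled, not that the protocol holds two competing targets. The inference needed is short: the table follows closely in the same section, counts the same unit, and shows 250 beside a second 250. The suggestion that 250 might be the true total, with the table at fault, has little support, because the table adds up exactly by site and by period at 250 per arm.

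**Conclusion.** The observation is accurate but leads to no change in the plan. The sentence leaves its arm unnamed, and its 250 equals one arm of a table that plans 500 families, 50 + 50 at each of five sites. The factor of two appears only if the sentence is taken as a two-arm total, which it does not claim to be.

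This is a clerical gap in labelling and not an arithmetic error. Those running the trial have an enrolment schedule by site, period and arm, and those analysing it will work from the families actually randomised. Adding an arm label would alter no enrolment, power, precision or analysis. The conclusion rests on taking the participant table as the operative target, which its exact row and column sums support, and on the fact that nothing in the protocol is calculated from the figure in the prose.
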